#### **7.5.4.9 Adverse Events**

All AEs will be recorded from the time the subject signs the informed consent through 30 days following the last administration of study drug. The determination, evaluation, reporting, and follow-up of AEs will be performed as outlined in Section 8.5. At each visit subjects will be asked about any new or ongoing AEs since the previous visit. Assessments of AEs will occur at each study visit.

Clinically significant changes from Baseline in physical examination findings, vital signs, clinical laboratory parameters, suicidal ideation and behavior, and ECGs will be recorded as AEs or SAEs, if appropriate. If feasible, additional PK samples will be collected whenever a potentially related SAE occurs.

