5.3 Study Day

Study day is calculated as (visit date – date of the first dose of investigational product + 1) if the date is on or after the first dose of investigational product; or (visit date – date of the first dose of investigational product) if the date is prior the first dose of investigational product.

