7.2 Missing Date Imputation Rules

The following conventions will be used to impute missing portions of dates for adverse events and concomitant medications.

1. Start Dates

- a. If the year is unknown, then the date will not be imputed and will be assigned a missing value.
- b. If the month is unknown, then:
 - i. If the year matches the first dose date year, then impute the month and day of the first dose date.
 - ii. Otherwise, assign “January.”
- c. If the day is unknown, then:
 - i. If the month and year match the first dose date month and year, then impute the day of the first dose date.
 - ii. Otherwise, assign the first day of the month.

2. Stop Dates

- a. If the year is unknown, then the date will not be imputed and will be assigned a missing value.
- b. If the month is unknown, then assign “December.”
- c. If the day is unknown, then assign the last day of the month.

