8.7.1 Adverse Events

Adverse Events will be assessed at all visits and throughout the course of the study. An AE will be considered a treatment emergent adverse event (TEAE) if it occurs or worsens in severity on or after the date of the first dose of study drug. An AE will be considered a UX007 emergent adverse event if it occurs or worsens in severity on or after the first date of

first dose of UX007 during the study. It is expected that the date of first dose of UX007 during the study will be the date of Randomization visit for the UX007 group and the date of Week 8 visit for the placebo group; however, the date of first UX007 dose actually received will be used.

UX007 emergent AEs will be summarized by SOC and preferred term during the period exposed to UX007 by treatment group and overall for all subjects who receive UX007. TEAEs will be summarized by SOC and preferred term during the course of the study by treatment group and overall for all subjects who receive study drug.

Exposure adjusted event incidence, defined as total number of occurrences of an event summed across all subjects in the group divided by the total observed time for events for subjects in the group, will be summarized for TEAEs and UX007 emergent AEs by SOC and preferred term by treatment group and overall.

During the double-blind placebo-controlled period; TEAEs will be summarized by treatment group and overall, and UX007 emergent AEs will be summarized by treatment group and overall. If no placebo subjects also receive UX007 during the double-blind placebo-controlled period, then there will only be one group for UX007 emergent AEs during the double-blind placebo-controlled period. During the open-label extension period, TEAEs and UX007 emergent AEs will both be summarized by treatment group and overall.

A high-level safety summary will display the numbers of subjects who experience one or more AEs in each of the following categories:

- All TEAEs and UX007 emergent AEs
- All treatment related TEAEs and UX007 emergent AEs
- Serious TEAEs and UX007 emergent AEs
- All treatment related SAEs and UX007 emergent SAEs
- Grade 3/4 TEAEs and UX007 emergent AEs
- TEAEs and UX007 emergent AEs leading to study discontinuation
- Fatal TEAEs and UX007 emergent AEs
- TEAEs and UX007 emergent AEs in the GI SMQ (see [Appendix C](#))
- Related TEAEs and UX007 emergent AEs in the GI SMQ

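### The SAP's partial start-date rule can move an adverse event known to have ended before first dose onto Day 1 and count it as treatment-emergent

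*SAP*

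**What the plan says.** SAP section 7.2 opens with its scope: "The following conventions will be used to impute missing portions of dates for adverse events and concomitant medications". Two start-date rules bring in the first dose date.

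- Month unknown (rule 1.b.i): "If the year matches the first dose date year, then impute the month and day of the first dose date".
- Day unknown (rule 1.c.i): "If the month and year match the first dose date month and year, then impute the day of the first dose date".

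Stop dates have separate rules, for example "If the day is unknown, then assign the last day of the month". Those rules act only on incomplete stop dates. Nothing in the section makes a start-date rule depend on the stop date, and nothing requires the imputed start to fall on or before the stop.

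SAP section 8.7.1 counts an event as treatment-emergent "if it occurs or worsens in severity on or after the date of the first dose of study drug". The same section requires a separate listing of events that are not treatment-emergent, and SAP Table 6 plans a listing of run-in events. Protocol section 7.5.4.9 sets the collection window: "All AEs will be recorded from the time the subject signs the informed consent through 30 days following the last administration of study drug". Protocol section 7.5.1 puts a 6-week Baseline Period between consent and randomization.

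**The concern.** Moving an uncertain onset to the first dose is a sensible, cautious convention when timing really is unknown. It stops being cautious when a recorded stop date shows that the event ended before dosing. The rule then overrides known data and creates a record whose start is later than its stop.

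Events that belong in the non-treatment-emergent listing would enter the treatment-emergent tables instead. In the UX007 arm, where SAP section 8.7.1 expects the first UX007 dose at Randomization, they would enter the UX007-emergent tables too. The exposure-adjusted rates in that section count occurrences, so they would rise as well. Safety measured by adverse event rates is a primary objective (SAP section 2.1), and the arms are small. With about 40 subjects at 3:1, the arms are roughly 40 × 3/4 = 30 and 40 × 1/4 = 10. One subject wrongly counted in a table row, with no other event in that row, moves the incidence by 1/30 = 3.3 points on UX007 or 1/10 = 10 points on placebo.

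**Working it through.** No figure in the plan depends on this rule, so there is none to reproduce. The check applies the rule literally and then measures how often it could apply.

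**Step 1: one record.** The dates are illustrative: first dose 20 March 2016, recorded stop 10 March 2016. SAP section 5.3 makes the first dose date Study Day 1, through "date of the first dose of investigational product + 1" with the event dated on the dose day.

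| Recorded start | Imputed start | Study day | Treatment-emergent | Start after stop |
|---|---|---|---|---|
| day unknown, March 2016 | 20 March 2016 | 1 | yes | yes |
| day and month unknown, 2016 | 20 March 2016 | 1 | yes | yes |
| day unknown, February 2016 | 1 February 2016 | −48 | no | no |

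In the first two rows the duration is 10 − 20 + 1 = −9 days. The third row shows the limit: a partial start in an earlier month is unaffected.

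**Step 2: reach of the day-unknown rule.** Assumptions: a 42-day baseline, first dose equally likely on each day of a 365-day year, and onset uniform over baseline. Consider an event lasting *D* days with onset *k* days before first dose.

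- It has resolved before dosing if *k* ≥ *D*. This leaves 43 − *D* possible onset days for each first-dose date, or 365 × (43 − *D*) in the year.
- If first dose is on day *d* of its month, onset is in that month when *k* ≤ *d* − 1. The affected onset days number max(0, *d* − *D*).
- Summed over a month of *L* days, this is (*L* − *D*)(*L* − *D* + 1)/2. The year has seven months of 31 days, four of 30 and one of 28.

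For *D* = 1: (7 × 465 + 4 × 435 + 378) / (365 × 42) = 5,373 / 15,330 = 35%.
For *D* = 7: (7 × 300 + 4 × 276 + 231) / (365 × 36) = 3,435 / 13,140 = 26%.

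| Event duration (days) | Affected / possible | Share |
|---|---|---|
| 1 | 5,373 / 15,330 | 35% |
| 3 | 4,679 / 14,600 | 32% |
| 7 | 3,435 / 13,140 | 26% |
| 14 | 1,720 / 10,585 | 16% |
| 21 | 593 / 8,030 | 7% |
| 28 | 54 / 5,475 | 1% |

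The share falls because a longer event must start earlier to end before dosing, and so is less likely to start in the month of first dose.

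**Step 3: reach of the month-unknown rule.** Only onsets in the previous calendar year escape. For *D* = 1 these number 42 + 41 + … + 1 = 903, so the affected share is 1 − 903/15,330 = 94%. For *D* = 28 they number 28 × 15 + (14 + 13 + … + 1) = 420 + 105 = 525, so the share is 1 − 525/5,475 = 90%. These are shares of a record type (stop date known, start month not known) that may be rare or absent.

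**Step 4: the same record with a stop-date condition.** The stop of 10 March precedes first dose, so the first-dose rule no longer applies. Day unknown in March becomes 1 March 2016. Year-only becomes 1 January 2016. Both precede the stop, and neither is treatment-emergent. The second raises a new problem: 20 March minus 42 days is 7 February 2016, so an onset on 1 January falls before consent. Protocol section 8.5.4.1 defines adverse events as having onset after consent. A consent-date floor is therefore needed.

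**The case against.** The strongest reply is that SAP section 8.7.1 asks whether an event occurs or worsens on or after first dose and does not mention an imputed start. An event with an earlier recorded stop did neither, so a sensible programmer would not flag it. That reading is possible, but section 7.2 states its conventions as the ones to be used for adverse event dates, and no text says that a stop date takes precedence. A literal derivation gives the wrong flag.

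A second reply is that other controls will catch it. SAP section 7.1 sends missing data to Data Management, Protocol sections 8.4.1 and 8.4.2 describe CRF checks, and Protocol section 8.5.4.1 requires prompt documentation including duration. These should reduce the number of partial dates, and a start after its stop is easy to see. They do not change the rule for dates that stay partial.

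A third reply is that the impact is limited. This stands. SAP section 8.7 plans no inferential safety testing, the rule applies alike in both arms, and no efficacy analysis uses it.

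A reader might infer three stronger things that the documents do not support.

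- That 35% of all such events, or 94% where the month is missing, are misclassified. The first figure holds only for one-day events, and the second describes a record type that may not occur.
- That negative durations distort a reported result. No planned output uses event duration.
- That background antiepileptic drugs would be analysed as newly started. A drug still in use has no stop date, so this is a different gap. Under SAP section 8.7.7 such a drug is still reported as concomitant and loses only its prior flag, and no planned analysis identifies newly started drugs.

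**Conclusion.** The point holds in a narrow form. Rules 1.b.i and 1.c.i of SAP section 7.2 give a demonstrably wrong result when three conditions meet: the start date is partial, its known part matches the first dose date, and the stop date precedes first dose. The event then has a start after its stop and is counted as treatment-emergent instead of being listed as not treatment-emergent.

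The documents give no count of partial dates, so the number of misclassified events cannot be stated and could be zero. The shares in the working rest on uniform onset, an even spread of first-dose dates and a 42-day baseline. They describe reach within a class of records, not an expected number of errors. The conclusion about the rule itself does not depend on them. The effect is confined to safety and medication summaries. It is still worth correcting, because the rule is wrong as written and the change is small.

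**What to change.** Amend SAP section 7.2 along these lines:

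- Impute the first dose date as the start only if the stop date, after its own imputation, is missing, ongoing, or on or after first dose.
- Otherwise set the start to the earliest date consistent with the recorded parts. For an adverse event, this must not be before the consent date.
- Require the imputed start to be on or before the stop.
- Classify such an adverse event as not treatment-emergent, and such a medication as prior only.

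As a separate, minor addition, state in SAP section 8.7.7 that a medication recorded as in use at Screening keeps its prior flag whatever its imputed start date.

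The cost is a few sentences in the SAP and a short condition in the derivation code. No new data are needed.

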7.3 Unscheduled or Early Termination Visits

In general, data collected by study visit will be summarized using the visit number specified in the database. Outcomes scheduled at a planned study visit but collected during an unscheduled visit or early termination visit will be mapped into the closest study visit based on the study day of the unscheduled visit or early termination visit, and the schedule of events in the protocol.

For outcomes where both the planned study visit and an unscheduled visit or early termination visit corresponding to that study visit are available, the planned study visit measurement will be used for the analysis.

All safety data including the planned study visits and unscheduled/early termination visits will be included in the shift tables.

All data will be included in the data listings and outcomes measured during unscheduled visits and early termination visits will be marked as acquired during an unscheduled visit.

Observable seizure frequency will be mapped to visits as described in Section [5.7.1](#).

7.4 Analysis Software

Data manipulation, tabulation of summary statistics, graphical representations and estimation of model parameters will be performed primarily using SAS (release 9.4 or higher) for Windows. If the use of other software is warranted, the final clinical study report will detail what software was used and for what purposes. Scoring software from Cambridge Cognition (Cambridge, UK) will be used to score the CANTAB instrument described in Section [5.8.1](#). T-score Based scoring software from QualityMetric Inc. (Lincoln, RI) will be used to score the SF-12 and SF-10 Health Survey instruments described in Sections [5.8.6](#) and [5.8.7](#) respectively.

7.5 Coding of Events and Medications

Adverse events will be coded to standardize presentation of AEs and TEAEs. AEs will be mapped to the Medical Dictionary for Regulatory Activities (MedDRA) system for reporting system organ classes and preferred terms.

Concomitant medications will be coded using the World Health Organization Drug Dictionary (WHO-DD).

8 STATISTICAL METHODS OF ANALYSIS

8.1 General Principles

During the Double-Blind Placebo-Controlled Treatment Period, efficacy analyses will be based on the Efficacy Analysis Set or the Per Protocol Analysis Set. During the open label period, efficacy analyses will be based on the Extension Set. Safety analyses will be based on the Safety Analysis Set. Unless stated otherwise, statistical tests will be 1-sided hypothesis tests performed at the 5% level of significance and confidence intervals will be 2-sided 90% confidence intervals. Continuous variables will be summarized by number of subjects and mean, standard deviation (SD), median, minimum, and maximum values. Categorical variables will be summarized by number and percentage of subjects.

Analyses and summaries by study period will be done for the following time periods:

- Double-blind placebo-controlled treatment period: after the date of the randomization visit until the date of the week 8 visit
- Open-label extension period: after the date of the week 8 visit until the date of the week 52 visit
- Dose exploration period: after the date of the week 26 visit until the date of the week 36 visit

Overall analyses and summaries will include all subjects and ignore treatment assignment.

For logarithmic transformations of seizure frequency, the natural logarithm will be used and a value of 1 will be added prior to performing the transformation.

For analyses and summaries of subjects while taking UX007, the time while taking placebo will be excluded and the original baseline will be used for all subjects regardless of which treatment was taken during the double-blind placebo-controlled treatment period.

Graphical displays of select study endpoints will be completed and include both observed study data and modeled analyses. Arithmetic means, least square means (LSM), and appropriate measure of dispersion (e.g., standard deviation, standard error) or confidence intervals may be displayed in figures.

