8.7 Safety Analyses

All safety analyses will be based on the Safety Analysis Set. In general safety analyses will be completed using summary statistics, graphs or subject listings. No planned inferential testing of safety endpoints is planned. If after the planned analysis it is determined by the medical writer and study medical monitor that inferential tests of significance may help to provide context for safety information these tests may be performed and identified in the CSR. Summaries will be done by study period and overall.

Analyses and summaries will be performed by study period, by treatment group, for subjects while taking UX007, and overall.

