Table	CANTAB Spatial Working Memory Strategy – Week 8 Analysis – Summary – Efficacy Analysis Set – CANTAB
Table	CANTAB – Change from Baseline – Week 8 Analysis – GEE – Efficacy Analysis Set – CANTAB
Table	CANTAB – Change from Baseline – Week 8 Analysis – GEE – Per Protocol Analysis Set – CANTAB
Table	6MWT Distance (meters) – Week 8 Analysis – Summary – Efficacy Analysis Set – 6MWT
Table	6MWT Distance (percent predicted) – Week 8 Analysis – Summary – Efficacy Analysis Set – 6MWT
Table	Onset of PED – Week 8 Analysis – Summary – Efficacy Analysis Set – 6MWT

Output Type	Title
Table	6MWT – Change from Baseline – Week 8 Analysis – GEE – Efficacy Analysis Set – 6MWT
Table	Onset of PED – Week 8 Analysis – GEE – Efficacy Analysis Set – 6MWT
Table	GMFM-88 Total Score – Week 8 Analysis – Summary – Efficacy Analysis Set – GMFM-88
Table	GMFM-88 Total Score – Change from Baseline – Week 8 Analysis – GEE – Efficacy Analysis Set – GMFM-88
	Exploratory Efficacy Analyses
Table	Frequency of Seizure Types via Diary – Week 8 Analysis – Summary – Efficacy Analysis Set
Table	Frequency of Seizure Types via EEG – Week 8 Analysis – Summary – Efficacy Analysis Set
Table	CGI-S and CGI-I – Week 8 Analysis – Summary – Efficacy Analysis Set – CGI-I
Table	CGI-I – Week 8 Analysis – t-tests – Efficacy Analysis Set
Table	SF-10 – Week 8 Analysis – Summary – Efficacy Analysis Set – SF-10
Table	SF-12 v2 – Week 8 Analysis – Summary – Efficacy Analysis Set – SF-12
Table	SF-10 – Change from Baseline – Week 8 Analysis – t-tests – Efficacy Analysis Set
Table	SF-12 – Change from Baseline – Week 8 Analysis – t-tests – Efficacy Analysis Set
Table	CNS – Week 8 Analysis – Summary – Efficacy Analysis Set – CNS
Table	CNS – Change from Baseline – Week 8 Analysis – t-tests – Efficacy Analysis Set
	Safety Analyses of Adverse Events
Table	Overall Summary of Adverse Events – Safety Analysis Set
Table	Overall Summary of Adverse Events by Study Period – Safety Analysis Set
Table	Treatment Emergent Adverse Events by System Organ Class and Preferred Term – Safety Analysis Set
Table	Serious Treatment Emergent Adverse Events by System Organ Class and Preferred Term – Safety Analysis Set
Table	Treatment Emergent Adverse Events by System Organ Class, Preferred Term and Greatest Severity – Safety Analysis Set
Table	Treatment Emergent Adverse Events by System Organ Class, Preferred Term and Greatest Reported Relationship – Safety Analysis Set

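### The visit-date study periods in SAP 8.1 conflict with the SAP's first-dose rules: Day 1 falls in no safety period, and the Week 8 date is either misplaced or unassigned

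*SAP*

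**What the plan says.** SAP 8.1 (General Principles) defines the double-blind period as "after the date of the randomization visit until the date of the week 8 visit" and the extension as "after the date of the week 8 visit until the date of the week 52 visit". These definitions govern safety. SAP 8.7 states: "Analyses and summaries will be performed by study period, by treatment group, for subjects while taking UX007, and overall". Table 6 in SAP 9 lists "Overall Summary of Adverse Events by Study Period – Safety Analysis Set".

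SAP 8.7.1 works from dosing instead. An adverse event is treatment-emergent if it "occurs or worsens in severity on or after the date of the first dose of study drug". The date of first UX007 dose, it expects, "will be the date of Randomization visit for the UX007 group and the date of Week 8 visit for the placebo group", although the actual date is used to flag UX007-emergent events. SAP 6.5 places each subject in the double-blind safety summaries under the treatment first received.

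Two other sections also draw the boundary differently from SAP 8.1. SAP 5.4 counts compliance days from the first-dose date inclusive, and counts extension days from the Week 8 visit date inclusive. SAP 5.7.1 includes the randomization day in the titration diary window and closes the last double-blind window on the day before the Week 8 visit.

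Protocol 7.5.4.9 collects adverse events "through 30 days following the last administration of study drug".

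**The concern.** The day that the SAP expects to be the first day of dosing lies outside the double-blind period. The day on which it expects placebo subjects to start UX007 lies outside the extension. A third gap opens after the Week 52 visit, while events are still being collected.

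Safety is one of the two primary objectives (SAP 2.1), and the double-blind summary is the only safety comparison of UX007 with placebo. The whole-study tables by treatment group cannot take its place, because the placebo group's column then includes up to 44 weeks on UX007 (52 − 8). Protocol 5.3 names gastrointestinal distress among the most commonly reported adverse effects, so first-exposure days should be placed correctly.

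**Working it through.** **Inputs.** Period rules: SAP 8.1. Treatment-emergent rule and expected dose dates: SAP 8.7.1. Attribution: SAP 6.5. Week 8 window of ±3 days: Protocol 7.5.1. Collection window: Protocol 7.5.4.9. About 40 subjects at 3:1: SAP 3.1 and 3.3. The plan states no figure to reproduce.

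**Assumptions.** Randomization visit = first dose = Day 1, as SAP 8.7.1 expects. Week 8 visit = Day 8 × 7 + 1 = 57. Week 52 visit = last dose = Day 52 × 7 + 1 = 365, so collection ends on Day 365 + 30 = 395. SAP 8.1 does not say whether 'until' includes the end date, so both readings are shown. An event with onset on any day in the table is treatment-emergent.

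| Day | SAP 8.1, 'until' inclusive | SAP 8.1, 'until' exclusive | Dosing-based rule (see fix) |
|---|---|---|---|
| 1 | no period | no period | double-blind |
| 2–56 | double-blind | double-blind | double-blind |
| 57 (Week 8 date) | double-blind | no period | open-label |
| 58–364 | extension | extension | open-label |
| 365 (Week 52 date) | extension | no period | open-label |
| 366–395 | no period | no period | open-label |

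**Day 1.** It is unassigned on either reading, in both arms.

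**Week 8 date.** On the inclusive reading, an ex-placebo subject's event after the first UX007 dose that day is in the double-blind period, and SAP 6.5 puts it under placebo. SAP 8.7.1 treats a placebo subject receiving UX007 in the double-blind period as something that may or may not happen; on this reading it is the expected case. On the exclusive reading, the event is in no period.

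**Period length.** Under SAP 8.1 read inclusively, the double-blind period is Days 2–57, or 56 days. Under the dosing-based rule it is Days 1–56, also 56 days. With Week 8 on Day 54 or Day 60, both rules give 53 or 59 days. The window moves by one day and does not change length.

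**Size.** At 3:1, 40 subjects give 40 × 3/4 = 30 on UX007 and 40 × 1/4 = 10 on placebo. This is approximate, since SAP 3.3 notes that the first three subjects were randomized 1:1. SAP 8.7.1 counts a subject once per level of summary, so a boundary-day event changes incidence only if it is that subject's only event at that level in the period:

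- one placebo subject: 1/10 = 10 percentage points
- one UX007 subject: 1/30 = 3.3 percentage points

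**Exposure.** SAP 5.2 computes duration from the doses taken within each period, so by-period exposure inherits the same one-day shift.

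**The case against.** The strongest reply is that this is a date convention with limited consequences. Most of its parts stand as limits on the point.

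- **Events are not lost from the trial.** A reader might infer that Day 1 events disappear. They do not: the whole-study tables and listings keep them, and the treatment-emergent definition has no end date, so events after Week 52 stay there too. Only the by-period summaries lose them.
- **No direction is shown for Day 1.** A reader might infer that both boundaries favour UX007. The documents do not support that. Day 1 is dropped from both arms, and Protocol 7.4.2 gives placebo, also an oil, the same dose level and titration. Dropping a placebo subject's only event lowers placebo incidence by 10 points, against 3.3 points for a UX007 subject.
- **Charging the Week 8 date to placebo needs the inclusive reading.** That is the only reading with no gap at Week 8, but the SAP does not state it.
- **Visits last two days.** Randomization and Week 8 are both 2-day visits (Protocol 7.5.1), and open-label treatment follows completion of the Week 8 visit (Protocol 7.4). If the recorded date is the first day and dosing falls on the second, neither boundary problem arises for that subject.
- **There is partial cover elsewhere.** UX007-emergent flags use the actual dose date, so an ex-placebo event on the Week 8 date can be identified. On the inclusive reading it would still sit in the placebo column of the double-blind treatment-emergent summary.
- **No inferential safety testing is planned** (SAP 8.7), so the effect is on descriptive incidence.

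What does not stand is leaving the rule alone. It works only when the SAP's own expectation of same-day dosing fails, and SAP 5.4 and 5.7.1 already place these days differently.

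**Conclusion.** The point holds as a specification defect in the by-period safety and exposure summaries. With dosing on the visit date, as SAP 8.7.1 expects, Day 1 is in no period in either arm. The Week 8 date is either in the double-blind period under placebo or in no period, depending on how 'until' is read. Days after the Week 52 visit and within the collection window are in no period; that last gap concerns open-label time and does not touch the comparison with placebo.

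The shifts of about 10 and 3.3 points are what one qualifying subject would cause. They are not expected biases: the documents give no rate of boundary-day events, and the net direction at Day 1 is unknown. The diary-based seizure windows have their own rule in SAP 5.7.1, and the sample-size statement is unaffected.

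**What to change.** For safety and exposure summaries, replace the visit-date periods in SAP 8.1 with dosing-based ones:

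- **Double-blind period:** from the date of first dose of study drug, inclusive, to the day before the first open-label UX007 dose. For subjects who never receive open-label UX007, it runs through 30 days after the last dose.
- **Open-label period:** from the date of first open-label UX007 dose through 30 days after the last dose.
- **Switch day:** use onset time if it is collected; the documents do not say that it is. Otherwise, assign same-day events to the open-label period by a pre-specified rule.

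Leave the diary windows in SAP 5.7.1 unchanged. The cost is a short SAP edit and a change to the period derivation in the programs. There is a small downside: without onset times, a few events that began before the switch on that day would be assigned to open-label UX007.
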